7.6.4 INJECTION SITE EVALUATION

Outcomes of the injection site evaluations will be tabulated by visit.

[REDACTED]

7.6.8 CONCOMITANT THERAPIES/MEDICATIONS

Concomitant therapies/medications used at Screening and at each trial visit will be coded using the World Health Organization (WHO) drug dictionary and summarized by treatment group, Anatomical Therapeutic Chemical (ATC) second level term, and preferred name for the Safety population.

7.6.9 ECG

The results of the ECG data will be tabulated by visit.

■ [REDACTED]

■ [REDACTED]

[REDACTED]

[REDACTED]

[REDACTED]

[REDACTED]

[REDACTED]

■ [REDACTED]

[REDACTED]

[REDACTED]

[REDACTED]

[REDACTED]

[REDACTED]

[REDACTED]

[REDACTED]

[REDACTED]

[REDACTED]

[REDACTED]

[REDACTED]

[REDACTED]

[REDACTED]

[REDACTED]

[REDACTED]

■ [REDACTED]

[REDACTED]

[REDACTED]

[REDACTED]

[REDACTED]

[REDACTED]

[REDACTED]

[REDACTED]

■ [REDACTED]

[REDACTED]

[REDACTED]

[REDACTED]

[REDACTED]

[REDACTED]

[REDACTED]

[REDACTED]

[REDACTED]

[REDACTED]

[REDACTED]

■ [REDACTED]

[REDACTED]

[REDACTED]

[REDACTED]

[REDACTED]

[REDACTED]

[REDACTED]

[REDACTED]

■ [REDACTED]

[REDACTED]

[REDACTED]

- [REDACTED]
- [REDACTED]
- [REDACTED]
- [REDACTED]
- [REDACTED]
- [REDACTED]
- [REDACTED]
- [REDACTED]
- [REDACTED]

[REDACTED]

[REDACTED]

[REDACTED]

[REDACTED]

[REDACTED]

[REDACTED]

[REDACTED]

[REDACTED]

[REDACTED]

[REDACTED]

[REDACTED]

[REDACTED]

[REDACTED]

[REDACTED]

[REDACTED]

[REDACTED]

[REDACTED]

[REDACTED]

9 RECORDS MANAGEMENT

9.1 DATA COLLECTION

For this trial, all protocol-specified data will be recorded in the source documents, and data will be entered on the CRFs from the source documents. In addition to signature confirmation that a subject meets the study eligibility criteria, upon each subject's completion of the trial, the Investigator will sign a statement indicating that all pages of the subject's case report have been reviewed. Signature stamps and "per signatures" are not acceptable.

It is Revance's policy that the trial data be verifiable with the source data that necessitates access to all original recordings, laboratory reports, and other records for each subject. The Investigator must therefore agree to allow access to subjects' records, and source data must be made available for all trial data. Subjects (or their legal representatives) must also allow access to their medical records. Subjects will be informed of the importance of increased record access and permission granted by signature on the informed consent document prior to Screening.

Checks will be performed to ensure the quality, consistency, and completeness of the data. Instances of missing or un-interpretable data will be resolved with the Investigator or Study Coordinator. Data queries will be sent to the trial center. Site personnel will be responsible for providing resolutions to the data queries and for correcting the CRFs, as appropriate. All unused Revance source documents and binders must be returned to Revance upon completion of the trial.

The Investigator must keep written or electronic source documents for every subject participating in the clinical trial. The subject file that identifies the study in which the subject is participating must include the subject's available demographic and medical information including:

- Name
- Contact information
- Date of birth
- Sex
- Medical history
- Concomitant diseases
- Concomitant therapies/medication
- Study visit dates
- Performed examinations, evaluations, and clinical findings

- Investigational product administration
- AEs, SAEs, or pregnancy (as applicable)

Additionally, any other documents with source data, especially original printouts of data that were generated by technical equipment must be included in the subject's source document (e.g., laboratory value listings). All these documents must have at least the subject's initials, trial number, and the date of the evaluation.

The data recorded during the course of the trial will be documented in the CRF and/or the trial-specific forms. Before or at study termination, all data must be forwarded to Revance. The data will then be recorded, evaluated, and stored in anonymous form in accordance with data-protection regulations.

Subjects will authorize the use of their protected health information during the informed consent process in accordance with the applicable privacy requirements. Subjects who deny permission to use and disclose protected health information will not be eligible to participate in the trial. The Investigator will ensure that the trial documents forwarded to Revance, and any other documents, contain no mention of subject names.

Any amendments and corrections necessary will be undertaken in both the source documents and CRFs (as appropriate) and countersigned by the Investigator, or documented designee, stating the date of the amendment/correction. Errors must remain legible and may not be deleted with correction aids. The Investigator must state his/her reason for the correction of any data. In the case of missing data/remarks, the entry spaces provided in the CRF should be cancelled out so as to avoid unnecessary follow-up inquiries.

Regulatory authorities, the IRB/IEC and/or the Revance's Quality Assurance group (or designee) may request access to all source documents, CRFs, and other trial documentation for on-site audit or inspection. The Investigator must guarantee direct access to these documents. CRFs will be kept by Revance or an authorized designee in a secured area. Clinical data will be recorded in a computer format for subsequent statistical analyses. Data files will be stored on electronic media with a final master data file kept by Revance after descriptive and statistical analyses and reports have been generated and are complete.

9.2 FILE MANAGEMENT AT THE TRIAL CENTER

It is the responsibility of the Investigator to ensure that the trial center file is maintained in accordance with ICH Guidance for Industry E6 Good Clinical Practice: Consolidated Guidance, Section 8 – Essential Documents for the Conduct of a Clinical Trial.

9.3 RECORDS RETENTION AT THE TRIAL CENTER

It is a Revance requirement that all Investigators participating in clinical studies maintain detailed clinical data for one of the following periods:

- Country-specific requirements, or
- A period of at least 2 years following the last approval of a marketing application approved by a Regulatory Authority in an ICH region or until there are no pending or contemplated marketing applications in an ICH region, or,
- A period of two years after Revance notifies the Investigator that the data will not be submitted for review by any Regulatory Authority

The Investigator must not dispose of any records or essential documents relevant to this trial without either (1) written permission from Revance, or (2) providing an opportunity for Revance to collect such records. The Investigator shall take responsibility for maintaining adequate and accurate electronic or hard copy source documents of all observations and data generated during this trial. Such documentation is subject to inspection by Revance and relevant regulatory agencies. If the Investigator withdraws from the trial (e.g., relocation, retirement) all trial-related records should be transferred to a mutually agreed upon designee. Notice of such transfer will be provided to Revance in writing.

10 MONITORING, COMPLIANCE, AND QUALITY

All aspects of the trial will be monitored by Revance or authorized representatives of Revance according to Good Clinical Practices (GCP) and Standard Operating Procedures (SOPs) for compliance with applicable government regulations, (i.e., Informed Consent Regulations and Institutional Review Board regulations). [REDACTED]

[REDACTED]

[REDACTED]

[REDACTED]

[REDACTED]

[REDACTED]

[REDACTED]

11 ETHICS AND RESPONSIBILITY

This trial must be conducted in compliance with the protocol, the ICH Guidance for Industry E6 Good Clinical Practice: Consolidated Guidance and the applicable regulatory requirements. Investigators must submit all essential regulatory documentation, as required by local and national regulations (including IRB/IEC approval of the protocol and informed consent form) to Revance before investigational product will be shipped to the trial center.

■ [REDACTED]

[REDACTED]

[REDACTED]

[REDACTED]

[REDACTED]

[REDACTED]

[REDACTED]

[REDACTED]

[REDACTED]

[REDACTED]

[REDACTED]

[REDACTED]

[figure not shown]
[REDACTED]

[figure not shown]
- | [REDACTED]
- | [REDACTED]
- | [REDACTED]
- | [REDACTED]

[figure not shown]
[REDACTED]

[figure not shown]
[REDACTED]

[figure not shown]
[REDACTED]

[figure not shown]

[figure not shown]

[figure not shown]

[figure not shown]

[figure not shown]

[figure not shown]

[figure not shown]

[figure not shown]

[figure not shown]

[REDACTED]
[REDACTED]

[REDACTED] [REDACTED] [REDACTED]	[REDACTED] [REDACTED] [REDACTED] [REDACTED] [REDACTED] [REDACTED] [REDACTED]	[REDACTED] [REDACTED] [REDACTED]
[REDACTED]	[REDACTED] [REDACTED] [REDACTED] [REDACTED] [REDACTED] [REDACTED]	[REDACTED] [REDACTED] [REDACTED]
[REDACTED]	[REDACTED]	[REDACTED] [REDACTED] [REDACTED]
[REDACTED] [REDACTED]	[REDACTED] [REDACTED] [REDACTED] [REDACTED] [REDACTED] [REDACTED] [REDACTED]	[REDACTED] [REDACTED] [REDACTED]
[REDACTED] [REDACTED]	[REDACTED] [REDACTED] [REDACTED] [REDACTED] [REDACTED] [REDACTED] [REDACTED]	[REDACTED] [REDACTED] [REDACTED]

1. INTRODUCTION

This statistical analysis plan (SAP) describes the objectives of the study and the efficacy and safety assessments that are collected. The primary, secondary, and exploratory efficacy endpoints and the safety endpoints are defined, and the statistical methods used to analyze them are presented. Table shells for the planned end-of-text tables, figures, and listings are included following the text of the SAP.

2. STUDY OBJECTIVES

The study objective is to evaluate the efficacy and safety of a single treatment of DaxibotulinumtoxinA for Injection for the treatment of moderate to severe glabellar lines compared to placebo.

2.1. Overall Study Design and Plan

This is a phase 3, double blind, placebo-controlled, multi-center trial to evaluate the efficacy and safety of a single intramuscular (IM) treatment of DaxibotulinumtoxinA for Injection for the temporary improvement in the appearance of glabellar lines in adults compared to a placebo.

The duration is up to 38 weeks on trial, including a screening period of up to two weeks followed by a single treatment and a follow-up period of up to 36 weeks post-treatment. All patients will be followed for at least 24 weeks post-treatment. Starting at Week 24 post-treatment, patients will be followed until their wrinkle severity in the glabellar lines at maximum frown returns to baseline in both the Investigator Global Assessment-Facial Wrinkle Severity (IGA-FWS) and Patient Facial Wrinkle Severity (PFWS) assessments.

[figure not shown]

Revance Therapeutics, Inc.

Confidential

Page 9 of 47

2.3. Determination of Sample Size

2.4. Treatments Administered

Approximately 300 adult patients with moderate to severe glabellar lines will be enrolled.

3. Efficacy and Safety Assessments

The primary efficacy assessments will include investigator assessment of glabellar line severity and glabellar line improvement, and patient assessment of glabellar line severity and improvement.

3.1. Frown Wrinkle Severity – Patient and Investigator Global Assessment

Frown wrinkle severity is assessed by both the patient (Patient Frown Wrinkle Severity [PFWS]) and the investigator (Investigator Global Assessment Frown Wrinkle Severity [IGA-FWS]) using the same 4-point rating scale, as shown in Table 3.1.1-1.

The severity is assessed at maximum frown and at rest after maximum frown by both the patient and the investigator. The scores range from 0 = none to 3 = severe.

[figure not shown]
Table 3.1.1-1 Frown Wrinkle Severity

Rating Score	Frown Wrinkle Severity	Description
0	None	No wrinkles
1	Mild	Very shallow wrinkles
2	Moderate	Moderate wrinkles
3	Severe	Deep wrinkles

3.1.1. Primary Efficacy Endpoint

The **primary efficacy endpoint** is derived from the maximum frown scores obtained at Week 4, and is defined as achieving a score of 0 or 1 (none or mild) and an improvement of at least two points from baseline on both the IGA-FWS and PFWS scales concurrently. The response will be abbreviated as "2-point composite response" henceforth.

3.2. Additional Assessments

3.2.1. Patient Diary

Patients will capture their assessment of the appearance of the lines at maximum frown, in a diary for the initial 2-week post treatment period, using the 4 point severity scale given in Table 3.1.1-1.

3.2.2. Patient Global Satisfaction with Treatment Questionnaire

Patients will be asked how satisfied or dissatisfied they are with the treatment results using a 7 point scale at Week 4. This treatment questionnaire will be based on how the treated area of the face looks (see Table 3.2.2-2).

 Table 3.2.2-2
 Global Satisfaction with Treatment Questionnaire Scale

Rating Score	Wrinkle Improvement
0	Very Dissatisfied
1	Dissatisfied
2	Somewhat Dissatisfied
3	Neither Satisfied Nor Dissatisfied
4	Somewhat Satisfied
5	Satisfied
6	Very Satisfied

3.2.3. Global Aesthetic Improvement Scale

The Investigator and patient will assess the visual appearance (at maximum frown and at rest after maximum frown) of the glabellar line improvement from the baseline condition using the following 7 point severity Global Aesthetic Improvement Scale (GAIS, Table 3.2.3-3).

 Table 3.2.3-3
 Global Aesthetic Improvement Scale

Rating Score	Wrinkle Improvement
-3	Very Much Worse
-2	Much Worse
-1	Worse
0	No Change
1	Improved
2	Much Improved
3	Very Much Improved

3.2.5. Facial Age Self Evaluation

Patients will rate their perceived age on a Facial Age Self Evaluation (FASE) questionnaire and rate their perception of how old they think they look following the treatment (older than actual age, younger than actual age, actual age). These responses will be used as exploratory endpoints.

3.3. Safety Assessments

3.3.1. Adverse Events

All adverse events (AEs) will be recorded and classified on the basis of MedDRA terminology. AE severity will be graded as mild, moderate, or severe as defined in Section 6.1.2 of the protocol. AEs with an onset on or after the date and time of study treatment will be Treatment-emergent.

The safety endpoints derived from the AEs are:

- Frequency, severity and relationship to study drug of treatment-emergent adverse events during the first four weeks post treatment and the overall study duration
- Frequency, severity and relationship to study drug of treatment-emergent serious adverse events during the first four weeks post treatment and the overall study duration

3.3.3. Clinical Laboratory Data

As outlined in Table 3.3.3-4, non-fasting samples for hematology, chemistry, coagulation (prothrombin time) and urinallysis will be collected at Screening, Week 4, and at the Final

Evaluation Visit.

Table 3.3.3-4 Clinical Laboratory Tests

Serum Chemistry	Hematology	Urinalysis	Additional Tests
		Overall Assessment	
Glucose	Hemoglobin		Prothrombin time (PT)
Total bilirubin	Hematocrit	and Clinical	Urine Pregnancy (WOCBP only)
Alkaline	Red Blood Cell	Significance	
phosphatase	Count		
Blood urea	Platelet Count		
nitrogen			
Alanine	Leukocyte Count		
aminotransferase	(total)		
Aspartate	Leukocyte Count		
aminotransferase	(differential)		

WOCBP = Women of child-bearing potential

3.3.5. Vital Signs

Vital signs (i.e., body temperature, respiration rate, sitting radial pulse rate, and sitting systolic and diastolic blood pressures) will be obtained at the Screening and Treatment Visit (pre- and post-treatment), Week 2, Final Evaluation or Early Discontinuation Visits and at any visit where signs or symptoms of botulinum toxicity are reported.

3.3.6. Physical Examination

A physical examination, in addition to vital signs,

, general appearance, skin, neck (including thyroid), eyes, ears, nose, throat, heart, lungs,

abdomen, lymph nodes, and extremities will be conducted at Screening, Week 2 and Final Evaluation or Early Discontinuation Visits. Significant physical examination findings that are present prior to investigational product administration are to be included on the Medical History page.

Significant physical examination findings which meet the definition of an adverse event will be recorded on the adverse event page post-treatment.

3.3.7. 12-Lead ECG

At Screening and Week 4, a single standard supine 12-Lead ECG will be obtained.

[figure not shown]
3.3.8. Injection Site Evaluation

[figure not shown]
Injection sites will be evaluated at the Screening Visit, Treatment Visit pre- and post-treatment, Follow-up Visits, and Final Evaluation Visit or Early Discontinuation Visit, if applicable. The assessment will be done as a global evaluation of the 5 injection sites (Table 3.3.8-5).

Table 3.3.8-5 Injection Site Evaluation

	Pres	ent?
Assessment Descriptor	Yes	No
Erythema		
Edema		
Burning or Stinging (sensation as described by patient)		
Itching (sensation as described by patient)		
Bruising		

[figure not shown]

4. Statistical Methods

All statistical programming will be performed using statistical analysis system (SAS) version 9.3 or higher.

4.1. Analysis Populations

4.1.1. Intent-to-Treat Population

All patients who are randomized and receive treatment will be included in the Intent-to-Treat (ITT) population. The summaries will be by treatment as randomized.

4.1.2. Per Protocol Population

The Per-Protocol (PP) population will include patients from the ITT population who complete the first 4-weeks of the study without a major protocol violation.

4.1.3. Safety Population

All patients who are randomized, receive treatment, and have provided at least one post-treatment safety assessment will be included in the Safety population. The summaries will be by treatment actually received.

4.2. Patient Disposition

The number and percentage of patients who have signed informed consent, been randomized, received treatment, and completed key visits will be tabulated by treatment group overall and by trial center (or pooled center, as appropriate) and included in a listing. Reasons for not completing the study will also be tabulated by treatment group and overall and by trial center using numbers and percentages; this data will also be included in a listing. For those patients who are considered to have failed screening, the reason(s) for failure will be provided in a listing.

The number and percentage of patients included and excluded from the analysis populations (ITT, PP and safety) will be tabulated overall and for each treatment group. Reason(s) for exclusion from each population will be summarized and listed.

Major protocol deviations will be listed and summarized by treatment group.

4.3. Demographic and Baseline Characteristics

Descriptive statistics will be used to summarize demographic and baseline characteristics by treatment group and overall. Continuous variables will be summarized using the number of non-missing observations, mean, standard deviation, median, minimum and maximum. Categorical data will be summarized using the number and percentage of patients in each category. Demographic data include age, sex, race and ethnicity. Age in years will categorized as 18 to 45, >45 to 55, and >55 to 75 for summarizing by treatment group and overall. Baseline characteristics include Prior Botulinum Toxin Type A, Time Since Last Prior Botulinum Toxin Type A Injection, and Fitzpatrick Skin Type, as well as the baseline assessment of the efficacy questionnaires, PFWS, IGA-FWS, FLIS, Summaries will be produced for the ITT

and PP populations by randomized treatment; and, for the Safety population by actual treatment received.

4.4. Medical History

Medical history will be classified on the basis of MedDRA terminology, using the latest terminology at the time of database finalization. Medical history will be summarized by treatment group, system organ class, and preferred term, and will be listed.

4.5. Prior and Concomitant Medications

[figure not shown]
Prior therapies/medications recorded at Screening but no longer being taken, and concomitant therapies/medications recorded at Screening and still being taken or being taken at each trial visit, will be coded using the World Health Organization (WHO) drug dictionary and summarized by treatment group and overall, Anatomical Therapeutic Chemical (ATC) second level term, and preferred name for the Safety population. Prior and concomitant medications will be summarized separately.

[figure not shown]
4.6. Efficacy Analyses

Descriptive statistics will be provided for all efficacy variables at all timepoints by treatment group.

[figure not shown]
alysis
ave a 2-point composite response at Week 4 will be compared
nd placebo
As a sensitivity analysis, the primary analysis
Tio a sensitivity analysis, the primary analysis
will be provided. The point estimates for the difference
will be provided. The point estimates for the difference
culated

4.8. Safety Analyses

Safety summaries and analyses will be performed on the safety population. Descriptive statistics will be presented to summarize the safety data.

4.8.1. Extent of Exposure

All patients receive one administration of investigational product. The sum of volume of investigational product injected and the volume of investigational product injected at each of the five injection sites will be summarized by treatment group using descriptive statistics (number of non-missing observations, mean, median, minimum, maximum, and standard deviation).

4.8.2. Injection Site Evaluations

The injection site evaluations will be summarized using number and percentage of patients reporting the presence of each item (Erythema, Edema, Burning or Stinging, Itching and Bruising) by treatment group and visit, as well as the number and percentage of patients with a reaction at any post-treatment visit. In addition, the number and percentage of patients reporting any injection site item will be summarized by treatment group, and by visit as well as at any post-treatment visit. Additionally, the number and percentages of patients with the specified item will be summarized according to the first visit at which the reaction was present.

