4.5.6 INJECTION SITE EVALUATION

Injection sites will be evaluated at the Screening Visit, Treatment Visit pre- and post-treatment (to determine if there is an immediate reaction to the investigational product), Follow-up Visits, and Final Evaluation Visit or Early Discontinuation Visit, if applicable. The assessment will be done as a global evaluation of the 5 injection sites (Table 4).

Table 4: Injection Site Evaluation

Assessment Descriptor	Present?	
	Yes	No
Erythema		
Edema		
Burning or Stinging (sensation as described by subject)		
Itching (sensation as described by subject)		
Bruising		

[REDACTED]

[REDACTED]

[REDACTED]

[REDACTED]

[REDACTED]

[REDACTED]

[REDACTED]	
[REDACTED]	[REDACTED]
■	[REDACTED]
■	[REDACTED]
■	[REDACTED]
■	[REDACTED]

[REDACTED]

[REDACTED]	[REDACTED]	[REDACTED]	[REDACTED]
[REDACTED]	[REDACTED]	[REDACTED]	[REDACTED]
[REDACTED]	[REDACTED]	[REDACTED]	[REDACTED]
[REDACTED]	[REDACTED]	[REDACTED]	[REDACTED]
[REDACTED]	[REDACTED]	[REDACTED]	[REDACTED]

[REDACTED]

[REDACTED]

[REDACTED]

[REDACTED]

[REDACTED]

[REDACTED]

[REDACTED]

[REDACTED]

[REDACTED]	■	[REDACTED]
	■	[REDACTED]
	■	[REDACTED]
	■	[REDACTED]
	■	[REDACTED]
	■	[REDACTED]
[REDACTED]	■	[REDACTED]
	■	[REDACTED]
	■	[REDACTED]
	■	[REDACTED]
	■	[REDACTED]
	■	[REDACTED]
[REDACTED]	■	[REDACTED]
	■	[REDACTED]
	■	[REDACTED]
	■	[REDACTED]
	■	[REDACTED]
	■	[REDACTED]
[REDACTED]	■	[REDACTED]
	■	[REDACTED]
	■	[REDACTED]
	■	[REDACTED]
	■	[REDACTED]
	■	[REDACTED]
[REDACTED]	■	[REDACTED]
	■	[REDACTED]
	■	[REDACTED]

[REDACTED]

[REDACTED]

[REDACTED]

[REDACTED]

[REDACTED]

[REDACTED]

[REDACTED]

[REDACTED]

[REDACTED]

[REDACTED]

[REDACTED]	[REDACTED]
■	[REDACTED]
■	[REDACTED]
■	[REDACTED]
■	[REDACTED]
■	[REDACTED]
■	[REDACTED]

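### The any-visit injection-site rates in SAP 4.8.2 have no common time window, because follow-up after Week 24 depends on response; they also ignore the pre-treatment finding

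*SAP*

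**What the plan says.** SAP 4.8.2 sets out several descriptive summaries of the five Yes/No injection-site items. The first gives, by arm and visit, the "number and percentage of patients reporting the presence of each item", and continues: "as well as the number and percentage of patients with a reaction at any post-treatment visit". A second works at the any-item level: "the number and percentage of patients reporting any injection site item will be summarized by treatment group, and by visit as well as" at any visit after treatment. A third classifies patients with an item, who "will be summarized according to the first visit at which the reaction was present".

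On collection, SAP 3.3.8 states: "Injection sites will be evaluated at the Screening Visit, Treatment Visit pre- and post-treatment, Follow-up Visits, and Final Evaluation Visit". Protocol 4.5.6 gives the purpose of the pre- and post-injection check: "to determine if there is an immediate reaction to the investigational product".

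On follow-up, SAP 2.1 guarantees 24 weeks for everyone and then makes the length depend on outcome: "Starting at Week 24 post-treatment, patients will be followed until their wrinkle severity in the glabellar lines at maximum frown returns to baseline", on both the investigator and the patient scale. Protocol 4.2.5 and the synopsis agree, with Week 36 as the limit. Protocol 7.6.4 plans only a by-visit tabulation, so the cumulative count is an addition made in the SAP.

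**The concern.** There are two separate gaps, and they have different consequences.

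The first is the window. A cumulative rate grows with the number of occasions on which the item can be recorded. After Week 24 that number depends on how long the effect lasts. If the active treatment outlasts placebo, active patients will more often be examined at Weeks 28, 32 and 36, and the any-visit percentages will cover different periods in the two arms. The adverse-event endpoints (SAP 3.3.1, Protocol 7.6.1) have a four-week window beside the full-duration one. The cumulative injection-site count has no such window.

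The second is the label. An item already present before the needle and still present afterwards is counted as a reaction. The other main safety summaries refer to the pre-treatment state: adverse events by onset, laboratory values by change and shift from Screening, vital signs and ECG by change from Screening. The any-visit injection-site count does not, although the pre-treatment evaluation is collected.

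At stake is one headline tolerability percentage per arm. No efficacy result is involved.

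**Working it through.** The documents state no injection-site rate, no pre-treatment prevalence and no share of patients expected past Week 24, so there is no planned figure to reproduce. The values of *q*, *f*, *p* and *r* below are assumptions.

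**Number of evaluations** (visit schedule in the Protocol synopsis and 3.1.4)
- To Week 24: Day 0 post-treatment plus Weeks 1, 2, 4, 8, 12, 16, 20 and 24, which makes 9. Week 1 is taken to be a follow-up visit with a site evaluation.
- To Week 36: add Weeks 28, 32 and 36, which makes 12, or 3/9 = 33% more.

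**Effect of the window.** Let *q* be the chance that an item is recorded at one visit, equal in both arms, constant and independent across visits. Then P(any in *k* visits) = 1 − (1 − *q*)^*k*. Let all placebo patients stop at Week 24 and let a share *f* of active patients attend all three extra visits. The spurious difference is *f* × (P12 − P9).

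Worked for *q* = 1%: P9 = 1 − 0.99^9 = 8.65%; P12 = 1 − 0.99^12 = 11.36%; the difference is 2.71 points, and with *f* = 30% it is 0.30 × 2.71 = 0.81 points.

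| Assumed *q* | P9 | P12 | *f* = 10% | *f* = 30% | *f* = 100% |
|---|---|---|---|---|---|
| 0.2% | 1.79% | 2.37% | 0.06 | 0.18 | 0.59 |
| 0.5% | 4.41% | 5.84% | 0.14 | 0.43 | 1.43 |
| 1% | 8.65% | 11.36% | 0.27 | 0.81 | 2.71 |
| 2% | 16.63% | 21.53% | 0.49 | 1.47 | 4.90 |

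The last three columns are percentage points, from unrounded values. If some placebo patients also continue, *f* becomes the difference between the arms in the share continuing. With both arms cut at Week 24 the comparison is 9 against 9 and the artefact is 0.

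**With an early reaction rate.** If a share *r* of each arm has a reaction soon after injection, the any-visit rate is 1 − (1 − *r*)(1 − *q*)^8 to Week 24, with exponent 11 to Week 36. For *q* = 1% and *f* = 30%, *r* = 10% gives 17.69% against 16.95% (0.74 points), and *r* = 30% gives 35.98% against 35.41% (0.57 points). A high early rate shrinks the artefact.

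**Effect of pre-existing items.** Let *p* be the pre-treatment prevalence, with every such item persisting (an upper bound), and *r* the true incidence. The counted rate is *p* + (1 − *p*)*r*.
- True 10% in both arms, *p* = 1 / 3 / 5%: counted 10.9 / 12.7 / 14.5% in both arms, difference 0.
- True 20% against 10%: the 10-point difference becomes (1 − *p*) × 10 = 9.9 / 9.7 / 9.5 points.
- Chance imbalance in *p* between 200 and 100 patients has SD √[*p*(1 − *p*)(1/200 + 1/100)] = 1.2 / 2.1 / 2.7 points.

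Pre-existing items therefore raise the level in both arms. They do not produce an expected difference where there is none, and they slightly dilute a real one.

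**The case against.** The strongest reply is that much of what is wanted is already in the plan. The by-visit tables, on their natural reading, include the Screening and pre-treatment evaluations and so would show pre-treatment prevalence by arm. Through Week 24 they compare the arms on the same schedule. The first-visit table shows how many items first appeared at Weeks 28 to 36. Exclusion criterion 3 (Protocol 3.4.3) removes patients with skin disease, infection or inflammation at the sites. Clinically significant changes at the site go to adverse-event reporting (Protocol 6.1), which has an onset rule and a Week 4 window. The summaries are descriptive, and injection reactions would be expected early, inside the shared window. The table shells and SAP 4.9.2 to 4.9.4 are not visible, so a rule there cannot be excluded.

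Most of this stands, and it keeps the point small. It does not close it. By-visit percentages cannot be added up into a patient-level any-visit rate, the first-visit table works item by item and cannot rebuild the any-item rate, and the adverse-event route covers only clinically significant changes. The entry criterion does not name bruising, itching or stinging.

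A reader might infer that the plan makes no use of the pre-treatment record, that the rates are shown to be inflated, or that pre-existing findings make the arm comparison unfair. The documents support none of these. The by-visit table can display the pre-treatment record; no rate is given from which inflation could be shown; and randomisation balances pre-existing items in expectation. Only unequal follow-up affects the fairness of the comparison.

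**Conclusion.** The point holds as a minor one. As written, the two any-visit summaries in SAP 4.8.2 have no common window, and the arm with the longer response is likely to have more evaluations, up to 12 against 9. For an assumed background of 0.5-2% per visit, equal in the arms and independent between visits, the spurious difference is about 0.4-1.5 points if 30% of active patients go on to Week 36. It would be 1.4-4.9 points only if every active patient did so and every placebo patient stopped at Week 24. A reader might take 2.7 points, the figure for 1% per visit, as the likely size; it belongs to that extreme case. The true size cannot be found from the documents.

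The missing pre-treatment condition is a matter of labelling and level in both arms, and does not by itself favour either arm. Neither gap touches the primary analysis.

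**What to change.** In SAP 4.8.2:
- Report the any-visit rates, for each item and for any item, through the Week 24 visit, and make these the between-arm comparison. Keep the full-duration counts as supportive, so that later findings stay in the safety summary.
- Add a row for items absent at the pre-treatment Day 0 evaluation and present afterwards, beside the existing count of all presence.
- Show the pre-treatment prevalence of each item by arm.

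The cost is a few sentences and a few extra table rows; the data are already collected. The limitation is that the items are recorded only as Yes or No, so the new-item row cannot capture an item that was present before and became worse. That is why the all-presence count should stay.
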